8.3. Response Definitions

Symptom Response:	To be defined based upon a blinded review of symptom scores (pooled for all EV/RV-infected subjects without regard to treatment group assignment) that correlate to the time at which subjects report that they return to usual health (a daily global assessment question). Methodology for the correlation will be defined in the Statistical Analysis Plan. Symptom scores must be maintained at the defined level for at least 2 daily diary periods without any symptom relief medication during those 2 daily diary periods.
Time of Symptom Response:	The start of the first daily diary period in which Symptom Response is achieved and is maintained for at least 2 daily

Time to Symptom Response:	diary periods without any symptom relief medication during those 2 daily diary periods.
Ability to Perform All Normal Activities:	Time (hours) from first dose to the Time of Symptom Response.
Time of Ability to Perform All Normal Activities:	Subject reports a score of 10 on the 0-10 scale for ability to perform normal activities, which is maintained for at least 2 daily diary periods without symptom relief medication during those 2 daily diary periods
Time to Ability to Perform All Normal Activities:	The start of the first daily diary period in which the subject reports a score of 10 on the 0-10 scale for ability to perform normal activities, which is maintained for at least 2 daily diary periods without symptom relief medication during those 2 daily diary periods
Individual Symptom Response:	Time (hours) from first dose to the Time of Ability to Perform All Normal Activities
Time of Individual Symptom Response:	For each individual symptom (n=32), a score of \leq the maximum response value specified in the Symptom Response definition maintained for at least 2 daily diary periods without symptom relief medication during those 2 daily diary periods
Time to Individual Symptom Response:	The start of the first daily diary period in which the Individual Symptom Response is achieved and is maintained for at least 2 daily diary periods without symptom relief medication during those 2 daily diary periods
FLU-PRO Domain Response:	Time (hours) from first dose to Time of Individual Symptom Response

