8.4. Statistical Methodology

The statistical methodology is described briefly below and will be described in detail in the Statistical Analysis Plan.

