8.4.1. Efficacy Analyses

Efficacy analyses will be based on a population consisting of all subjects that received at least one dose of study drug and had laboratory-documented EV/RV infection (infected intent-to-treat or ITTI population). Laboratory-documented EV/RV infection is defined by identification of EV/RV in nasopharyngeal secretions by RT-PCR at baseline, Day 2 or Day 3. For time to event analyses a test of significance (as described in the following) will be performed with descriptive statistics provided including the use of Kaplan-Meier figures.

There will be one primary efficacy analysis:

- Time to Symptom Response for the NTZ treatment group will be compared to that of the placebo treatment group using a stratified Gehan-Wilcoxon test ($\alpha = 0.05$) where stratification will follow that used for randomization. Subjects without a Symptom Response being recorded will be treated as censored as of their last diary without a documented Symptom Response.

If the primary analysis is significant at the 0.05 level, a key secondary efficacy analysis will be formally evaluated at the 0.05 level as follows:

- Time to Ability to Perform All Normal Activities for the two treatment groups will be compared using a stratified Gehan-Wilcoxon test ($\alpha = 0.05$) where stratification will follow that used for randomization. Subjects without an Ability to Perform All Normal Activities response being recorded will be treated as censored as of their last diary without a documented Ability to Perform All Normal Activities response.

If both the primary analysis and the key secondary efficacy analysis are significant at the 0.05 level, another secondary efficacy analysis will be formally evaluated at the 0.05 level as follows:

- Proportions of subjects experiencing one or more complications of colds due to EV/RV infection will be compared between the treatment groups using a Cochran-Mantel-Haenszel test stratified by the randomization strata ($\alpha = 0.05$).

Exploratory analyses will be performed as follows:

- For each of the 32 individual FLU-PRO symptoms, Time to Individual Symptom Response for the NTZ and placebo treatment groups will be compared using the Gehan-Wilcoxon test.
- For each of the 6 FLU-PRO domains, Time to FLU-PRO Domain Response for the NTZ and placebo treatment groups will be compared using the Gehan-Wilcoxon test.

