### 8.3. Sample Size Justification

The Symptom Response definitions for this study will be derived from the subjects' FLU-PRO questionnaire responses as described in [Section 11.2.1](#). The FLU-PRO-derived endpoint is expected to track very closely to return to usual health status (a daily yes/no question in the FLU-PRO questionnaire), which in turn is expected to track very closely to ability to perform 100% of normal activities. We assume, therefore, that the cumulative distributions of time to Symptom Response for the placebo treatment group will closely reflect historical data from Romark Study RM08-3002 for time from first dose until the EV/RV-infected subjects report that they are able to perform 100% of usual activities (see placebo curve in chart below). Then, to calculate sample size, we assume that treatment with NTZ treatment should result in reduction of at least 48 hours in median time to symptom response. The following curves have been developed for determining sample size.

Based upon these curves, a sample size of 530 subjects with laboratory-confirmed EV/RV infection (i.e. 265 for each of the 2 groups) will provide 90% power to detect a statistically significant difference in the survival distributions between the NTZ and placebo groups (2-sided  $\alpha=0.05$ ). This calculation was performed for the Gehan rank test using SAS PROC POWER (SAS 9.4) with the curves shown above (proportion not recovering by the end of each day was used as input) and censoring at Day 21 (hour 504). Assuming that up to 12% of subjects will have incomplete data, we arrive at a sample size of 600 subjects in total, 300 per treatment group to yield at least approximately 530 with complete data (all EV/RV-infected subjects who receive at least one dose of study medication will be included in the primary analysis with subjects with incomplete data censored as of their last entry).

Based upon these calculations, the study will enroll at least 600 subjects with laboratory-confirmed EV/RV infection up to a maximum of 700 subjects with laboratory-confirmed EV/RV infection.

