### 11.2. Primary Efficacy Analysis: Time to Symptom Response

The primary efficacy analysis will be the comparison of the time from first dose of study medication to Symptom Response between treatment groups using Kaplan-Meier survival curves and a Gehan-Wilcoxon test stratified by (1) time from onset of illness to time of first dose of study medication (0-24, >24-≤36, or >36 hours from onset), (2) pre-enrollment use of symptom relief medication, and (3) presence of underlying lung condition including asthma, COPD, or past or present history of smoking. Separate Symptom Response definitions will be determined for ITTI subjects with no underlying lung condition and for ITTI subjects with underlying lung conditions. Time to Symptom Response will be calculated in the same way for the two groups and all ITTI subjects will be analyzed together.

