#### Definitions:

Symptom Response	The set of criteria to be defined based upon a blinded review of symptom scores (pooled for all ITTI subjects without regard to treatment group assignment) that correlate to the time at which subjects report that they return to usual health (a daily global assessment question). Methodology to be used for the derivation of the Symptom Response definition is described in Section 11.2.1 below. Symptom scores must be maintained at the defined level for at least 2 daily diary periods without any symptom relief medication during or between those 2 daily diary periods.
Time of Symptom Response	The start of the first daily diary period in which Symptom Response is achieved and is maintained for at least two daily diary periods without any symptom relief medication during or between those two daily diary periods.
Time to Symptom Response	Time (hours) from the first dose of study medication to the Time of Symptom Response.

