#### **11.2.2. Analysis of the Primary Efficacy Parameter**

The primary efficacy parameter, time to Symptom Response, will be derived as follows:

Event: Time of Symptom Response – time of the first dose

Censored: Time of last symptom assessment – time of the first dose

If Symptom Response is achieved at the time of the first symptom assessment diary record, the subject will be excluded from the analysis.

If Symptom Response is not achieved prior to a subject’s last available diary assessment, but the criteria are met at the last available diary assessment with no evidence of symptom relief medication intake during that diary period, time of Symptom Response will be considered to have occurred at the start of the last daily diary period.

Time to Symptom Response for the NTZ treatment group will be compared to that of the placebo treatment group using a Gehan-Wilcoxon test stratified by (1) time from onset of illness to time of first dose of study medication (0-24, >24-≤36, or >36 hours from onset), (2) pre-enrollment use of symptom relief medication, and (3) presence of underlying lung condition including asthma, COPD, or past or present history of smoking. The comparison will be graphically depicted using Kaplan-Meier curves.

Analysis Population(s): ITTI

Derived Variables: Event: Time of Symptom Response – time of first dose

Censored: Time of last symptom assessment – time of first dose

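### SAP 11.2.2 counts one qualifying last diary as a primary event and drops first-record responders, against the two-diary, all-infected definition; the size and direction of the effect are unknown

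*SAP*

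**What the plan says.** **Event.** Protocol 8.3: "Symptom scores must be maintained at the defined level for at least 2 daily diary periods without any symptom relief medication". SAP 11.2 dates the response at "The start of the first daily diary period in which Symptom Response is achieved and is maintained for at least two daily diary periods". SAP 11.2.1 calibrates the definition with two consecutive diaries required both for response and for return to usual health.

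**Censoring.** Protocol 8.4.1: "Subjects without a Symptom Response being recorded will be treated as censored as of their last diary without a documented Symptom Response". Protocol 8.1 and SAP 8.3 also censor incomplete data at the last entry.

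**Analysed set.** Protocol 8.1 puts all 600 subjects in the primary analysis. SAP 8.3 says "all EV/RV-infected subjects who receive at least one dose of study medication will be included in the primary analysis". SAP 11.2 says of the infected intent-to-treat (ITTI) population that "all ITTI subjects will be analyzed together".

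**SAP 11.2.2** adds two rules that are not in the protocol:
- A subject with no earlier response is an event, dated to the start of the last diary period, where the criteria were not met before, "but the criteria are met at the last available diary assessment with no evidence of symptom relief medication intake during that diary period".
- "If Symptom Response is achieved at the time of the first symptom assessment diary record, the subject will be excluded from the analysis".

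The same pair of rules stands in SAP 11.4.1 for the key secondary endpoint and in 11.5.1 to 11.5.3 for exploratory endpoints.

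**The concern.** Two analysts, one following the protocol and one following SAP 11.2.2, would produce different event flags and different analysis sets for the primary and key secondary endpoints. Under the SAP an unconfirmed diary counts as a sustained response. Randomised, dosed, infected subjects can also leave the analysis. Because response needs a second consecutive medication-free diary, that exclusion rests at least partly on data recorded after dosing. If either rule is used unequally in the two arms, the test result can change, and nothing in SAP 11.3 would show it.

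**Working it through.** **1. The plan's own figure.** 530 / (1 - 0.12) = 602.3, against 600 stated; 600 x 0.88 = 528. The inflation step reproduces. The step from the planning curves to 530 for 90% power cannot be checked, because the curves could not be read. The sizes below therefore use stand-in distributions.

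**2. The rules applied to one subject (assumed clock times).** First dose is at 10:00 on Day 1 and diaries are at 20:00. Only the last diary, on Day 12, qualifies.
- Protocol 8.4.1: censored at 11 x 24 + 10 = 274 h.
- SAP 11.2.2: event at 274 - 24 = 250 h.

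For a response at the first record there are two readings. If that record is the supervised pre-dose diary (Protocol 5.2), the confirming diary is post-dose. If it is the Day 1 evening diary, both are post-dose, and the period starts at 10 - 24 = -14 h, before first dose.

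**3. How many switch from censored to event.** Assumptions: exponential times with placebo median 302 h (Protocol Table 7), S(t) = 2^(-t/302); 12% stop diaries uniformly over Days 2-20; no isolated good days before recovery.
- S(24) = 0.9464, S(480) = 0.3323, S(504) = 0.3145.
- Completers: 0.88 x (0.3323 - 0.3145) = 1.57%.
- Early stoppers: 0.12 x (0.9464 - 0.3323) / 19 = 0.39%.
- Total 1.96%, about 12 of 600.

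Isolated good days on 5, 10 or 15% of diaries raise this to 3.37, 4.21 and 4.44%. If each diary is completed with 87% probability (the compliance reported for RM08-3004 in Protocol section 3), the count is 14-30 of 600.

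**4. Last-diary rule alone, balanced random stopping.** Assumptions as in step 3, 300 + 300 subjects, Gehan test stratified on 12 equal strata (3 x 2 x 2), 2,000 trials per row. Rejection rates are protocol rule / SAP rule.

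| Isolated good days | Null, 302 v 302 h | 302 v 215 h | Mean switched of 600 (null) |
|---|---|---|---|
| 0% | 5.3 / 5.4% | 88.1 / 88.9% | 11.7 |
| 5% | 5.0 / 5.1% | 87.1 / 87.8% | 20.2 |
| 10% | 4.2 / 4.2% | 81.7 / 82.2% | 25.3 |
| 15% | 5.1 / 5.3% | 72.8 / 73.5% | 26.4 |

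The verdict at 0.05 differs in 0.5-1.4% of null trials and 1.4-3.5% of trials at 302 v 215 h.

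**5. Both rules together, including unequal use.** Assumptions: lognormal times (log-SD 1.157), medians 302 v 214 h, 3% transient good or bad days, 300 per arm, unstratified Gehan test, 5,000 trials (simulation error about 0.3-0.4 point). Arm percentages are placebo / NTZ.

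| Scenario | SAP rules | Two-diary, all ITTI |
|---|---|---|
| 12% random stopping, power | 91.3% | 91.8% |
| 12% random stopping, type I error | 5.0% | 5.4% |
| 12% / 12% stop on first good day, power | 91.0% | 89.0% |
| 4% / 12% stop on first good day, power | 94.7% | 69.8% |
| 12% / 4% stop on first good day, power | 84.6% | 97.6% |
| First-record responders 3% / 3%, power | 90.9% | 87.9% |
| First-record responders 2% / 5%, power | 90.8% | 96.6% |

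The two unequal-stopping rows also carry 6% random stopping per arm. The unequal rows differ by 94.7 - 69.8 = 24.9, 97.6 - 84.6 = 13.0 and 96.6 - 90.8 = 5.8 points, not all in one direction. Under the null, with 10% transient good days and 4% / 12% stopping on a good day, type I error is 10.2% under the SAP rules (mean z +0.68 toward NTZ) and 8.5% under the two-diary rule (mean z -0.53, away from it).

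**6. Do the planned sensitivity analyses cover this?** SAP 11.3.1 assigns 21 days to subjects who discontinued before responding, but takes its variables from 11.2, so a deemed last-diary response still counts. SAP 11.3.2 (per protocol) and 11.3.3 (chromaturia) keep both rules. Listing 16.2.3 will show exclusions, but no analysis restores those subjects.

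**The case against.** Protocol 8.4 leaves detail to the SAP: "The statistical methodology is described briefly below and will be described in detail in the Statistical Analysis Plan". Both rules also have a practical origin. If diaries end on Day 21, a response first seen that day cannot be confirmed. A response at the first record would be dated at or before first dose. This explains the rules, but changing what counts as an event and who is analysed is more than detail, and the last-diary rule applies on any day.

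The first record is most naturally the supervised baseline diary. Few primary exclusions would then follow, since entry requires moderate or severe rhinorrhea (Protocol 4.1). That is fair for the primary endpoint. There is no entry criterion on the activity score, so the number for the key secondary endpoint is unknown.

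The strongest point is that the two-diary rule is not neutral either. Censoring people who stop because they feel well is informative, and step 5 shows the two rules biased in opposite directions under unequal stopping. This stands. It means that both analyses should be prespecified, and it leaves the contradiction in place.

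**Conclusion.** The contradiction is certain from the text, for both rules and for the primary and key secondary endpoints. Its numerical effect is not known. With random stopping balanced by arm, about 2-4% of subjects change status, and power and type I error move by about 1 point or less. With heavier but balanced use of the rules, power moves by 2-3 points. With assumed arm differences it moves by 6-25 points in either direction. The distributions, the stopping patterns and the shares of first-record responders are all assumptions.

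A reader might infer three stronger things that the documents do not support:
- *That the SAP rules favour NTZ or inflate type I error.* Type I error stays near 5% when stopping is balanced. When it is not, neither rule is free of bias.
- *That the effect is negligible.* That holds only if few subjects are affected and the arms are alike, which the documents do not establish.
- *That nearly all last-diary events fall on Day 21 and so matter little.* The base-case share, 1.57 / 1.96 = 80%, is model output assuming full diary completion.

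The event time of the key secondary and usual-health endpoints is a separate, minor mismatch. SAP 11.4.1 and 11.5.3 use the diary entry, and Protocol 8.3 uses the start of the period. The SAP revision history records a clarification of these definitions in version 1.1. For the key secondary endpoint, events move by 24 h in both arms, and in simulation the verdict differed in at most 1.1% of trials.

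**What to change.** Before unblinding:
1. In SAP 11.2.2 and 11.4.1, with matching wording in 11.5.1 to 11.5.3, make the protocol's two-diary, all-ITTI analysis the primary rule and report the last-diary and first-record rules as a labelled sensitivity analysis. If the SAP rules stay primary, amend the definitions to match them and prespecify the protocol-rule analysis.
2. Report by arm the number of single-last-diary events and of first-record responders.
3. State which diary is the first record, and give a time convention for any response whose period starts at or before first dose (for example, an event tied at the lowest rank). If an exclusion is kept, base it on the pre-dose baseline score alone and run the analysis both ways.
4. Reconcile the end of the diary: Day 21 in Protocol 5.10 and SAP 8.2, but Day 22 (+3) in footnote 7 of Protocol Table 13 and SAP Table 17. Say whether a Day 22 entry may confirm a Day 21 response.
5. Separately, align the event time of the key secondary and usual-health endpoints between the two documents.

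The cost is wording, minor programming, one or two extra runs, and slightly more censoring (about 2-4% of subjects under the balanced assumptions). Power falls somewhat if first-record responders kept at the lowest rank are numerous: 90.9 - 87.9 = 3.0 points at 3% per arm, with all rules changed together.

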### 11.3. Sensitivity Analyses of the Primary Efficacy Analysis

#### 11.3.1. Sensitivity Analysis Assuming Time of Symptom Response of 21 Days for Discontinued Subjects

Repeat the primary efficacy analysis assuming a time of Symptom Response of 21 days (504 hours from first dose of study medication) for subjects who discontinued the study prior to achieving Symptom Response.

Analysis Population(s): ITTI

Derived Variables: See [Section 11.2: Primary Efficacy Analysis](#)

#### 11.3.2. Sensitivity Analysis for a “Per Protocol” Subset

Repeat the primary efficacy analysis for the Per Protocol population.

Analysis Population(s): ITTI

Derived Variables: See [Section 11.2: Primary Efficacy Analysis](#)

#### 11.3.3. Sensitivity Analysis Excluding Subjects Reporting Chromaturia

Repeat the primary efficacy analysis for the ITTI population excluding NTZ-treated subjects who reported chromaturia as an adverse event during the study.

Analysis Population(s): ITTI excluding NTZ-treated subjects who reported chromaturia

Derived Variables: See [Section 11.2: Primary Efficacy Analysis](#)

### 11.4. Secondary Efficacy Analyses

If the primary analysis is significant at the 0.05 level, the secondary efficacy analysis of Time to Ability to Perform All Normal Activities will be formally evaluated at the 0.05 level. If the primary analysis and the secondary efficacy analysis of Time to Return to Normal Activities are both significant at the 0.05 level, the secondary efficacy analysis of Proportions of Subjects Experiencing Complications of Colds will be formally evaluated at the 0.05 level. If any of these analyses is not significant at the 0.05 level, the subsequent analyses or analysis will be performed as exploratory.

#### 11.4.1. Time to Ability to Perform All Normal Activities

Definitions:

Ability to Perform All  
Normal Activities

Subject reports a score of 10 on the 0-10 scale for ability to perform normal activities and maintains the score for at least two consecutive daily diary periods without symptom relief medication during or between those two daily diary periods

Time of Ability to Perform

All Normal Activities	The time of the first daily diary entry in which the subject achieves Ability to Perform All Normal Activities
Time to Ability to Perform All Normal Activities	Time (hours) from first dose to the Time of Ability to Perform All Normal Activities

### Variables Used for the Analysis

The analysis will require the following variables:

**Table 7: Variables Used for Analysis of Time to Ability to Perform All Normal Activities**

Variable	Source	Format/Notes
Date and time of first medication intake	CRF	
Date and time of completion for each ability assessment record	Subject diary	
Ability to perform normal activities score	Subject diary	The ability to perform normal activities score will be recorded by the subject on a 0-10 scale. In the event that the score was not recorded at a specified time point (e.g., Day 2), the missing data will not be imputed.
Date and time of symptom relief medication intake	Sponsor-provided listing	The list of symptom relief medications will be selected from the listing of all concomitant medications prior to unblinding.

### Analysis

The efficacy parameter, Time to Ability to Perform All Normal Activities, will be derived as follows:

Event: Time of Ability to Perform All Normal Activities – time of the first dose

Censored: Time of last ability assessment – time of the first dose

If Ability to Perform All Normal Activities is achieved at the time of the first ability assessment diary record, the subject will be excluded from the analysis.

If the subject does not achieve Ability to Perform All Normal Activities prior to the subject's last available diary assessment, but records a "10" for ability to perform all normal activities at the last available diary assessment with no evidence of symptom relief medication intake during that diary period, time of Ability to Perform All Normal Activities will be considered to have occurred at the time of the last available diary assessment.

Time to Ability to Perform All Normal Activities for the NTZ treatment group will be compared to that of the placebo treatment group using a Gehan-Wilcoxon test stratified

by (1) time from onset of illness to time of first dose of study medication (0-24, >24-≤36, or >36 hours from onset), (2) pre-enrollment use of symptom relief medication, and (3) presence of underlying lung condition including asthma, COPD, or past or present history of smoking. The comparison will be graphically depicted using Kaplan-Meier curves.

Analysis Population(s): ITTI

Derived Variables: Event: Time of Ability to Perform All Normal Activities – time of first dose

Censored: Time of last ability assessment – time of first dose

